Each group will have 10 participants. Group 1 will undergo application of three normal saline soaked lap sponges to the surgical site, while Group 2 will undergo application of three TXA soaked lap sponges to the surgical site. After the abdominal skin and subcutaneous tissue is raised, the area will be irrigated, and hemostasis achieved using electrocautery. These steps are currently preformed with every panniculectomy. After hemostasis and irrigation, the soaked lap sponges will be unfolded and placed beneath the two lateral portions as well as the central area of the flap for 3 minutes. The lap sponges will not be “rung out” prior to placement. The time for TXA application is based on previous studies. The lap sponges will be removed after

Reading Hospital – Tower Health Research Protocol

three minutes. The surface area under the flap will be measured from the xiphoid process to the pubis, from the Xiphoid process to each anterior superior iliac spine (ASIS) and across from one ASIS to the other. These measurements will be used to calculate the surface area under the flap. These measurements will only be used in data collection and do not affect the principle aim of the study. The remainder of the surgical procedure will be the same for each patient. As currently practiced, two 15 round Blake drains will be placed for each patient. Patients will stay overnight for routine post-operative monitoring including vital signs and drain output or may be discharged home the same day of surgery if medically fit. Patients will also be monitored clinically at each post-operative visit for signs of post-operative hematoma or seroma.

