After discharge, post-operative drain output will be monitored and recorded by the patient on the provided drain documentation sheet. This does not differ from the current standard of care regarding drain output recordings. All patients who receive a post-surgical drain are asked to document output. All patients will be educated on routine drain care and recording drain output prior to surgery, as well as post-operatively. Each patient will be given a standardized form to record their drain output. Post-operative drain output will be assessed during each post-operative visit. Drains will be removed when output is less than 30cc per drain in 24-hour period. Patients will track their 24-hour total drain output by recording the 24-hour total output at 10 am every day. If the output exceeds the drain capacity during the 24-hour interval but before the 10am empty time, the patient will empty the drain when full, record that output, allow the drain output to reaccumulate, and empty-record the drain output again at 10am or again when the output exceeds the drain capacity. The individual outputs recorded during the 24-hour interval will then be totaled to determine one output sum for the entire 24-hour time period between 10am time intervals. Each drain bulb will accommodate a maximum of 60cc of postoperative fluid. When less than 30 cc per drain in 24-hour period, patients will call to schedule drain removal. Drain recording policies do not differ from non-study patients. All post-operative panniculectomy patients are required to record their drain output. Each patient will be evaluated one week, three weeks, and eight weeks following their procedure to assess overall wound healing, post-operative fluid collections, drain output and overall well-being.

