Data analysis for this project will consist of several parts. First it is important to analyze differences between the randomized control and treatment arms to test for bias. In order to do this, goodness of fit tests (GOF) will be performed on demographic variables such as age and gender. While the sample sizes are expected to be low, 10 for each arm, nonparametric tests consisting of Fisher's exact for discrete variables and Mann-Whitney U tests for continuous level data will be used. An omnibus p-value of 0.20 will be used to ensure there is no bias present in the samples. Secondly, efficacy analysis will be conducted on the outcome variables (drain output per day, total drain output, etc.) by use of Mann-Whitney U test. Statistically significant findings would be for a p-value less than 0.05 on any test. The samples are not expected to be large enough for the use of parametric measures so non-parametric methods will be used.

With a small sample of 10 patients per arm this analysis is viewed to be exploratory, and there will be no statistical corrections applied for multiple comparisons. Results of the GOF and efficacy analysis will be prepared and placed into tables for each group. In addition to the analysis mentioned above, power analysis will also be used to calculate the observed power for those tests with significant differences as well as to determine a sample size for those efficacy endpoints that did not achieve statistical difference. These power estimates will accompany the results in a separate table. Power analysis will be based on single tail alternative hypothesis with a power (1-B) of 80 percent and a p-value of 0.05. As this is an exploratory study, there will

Reading Hospital – Tower Health Research Protocol

be no interim analysis for efficacy or futility. The trial will be stopped after inclusion of twenty patients.

E. PROTECTION OF HUMAN SUBJECTS

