3. POTENTIAL BENEFITS OF THE PROPOSED RESEARCH TO THE SUBJECTS AND OTHERS

- Our study aims to demonstrate a difference in hematoma rates as well as drain output between patients undergoing panniculectomy using topical tranexamic acid vs. normal saline. As a pilot study, these results could be used to encourage a larger investigation of the use of TXA in panniculectomy patients.

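### The significance rule covers any test on an open outcome list, with no primary outcome or sidedness, and it also gates the power table; the hematoma aim in E.3 exceeds what 10 per arm can show

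*Combined protocol and SAP*

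**What the plan says.** All analysis rules are in section D of the combined protocol and SAP. Efficacy is covered by one sentence: "efficacy analysis will be conducted on the outcome variables (drain output per day, total drain output, etc.) by use of Mann-Whitney U test". The decision rule follows: "Statistically significant findings would be for a p-value less than 0.05 on any test". The plan is open about its status: "this analysis is viewed to be exploratory, and there will be no statistical corrections applied for multiple comparisons".

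A table of power results is then planned. Its stated purpose is this: "calculate the observed power for those tests with significant differences as well as to determine a sample size for those efficacy endpoints". The endpoints meant at the end of that phrase are the ones without a significant result. The table's settings are 80% power and 0.05, and "Power analysis will be based on single tail alternative hypothesis". That is the only statement of sidedness in the plan.

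No outcome is called primary. Section D says of the flap measurements that they "do not affect the principle aim of the study", but that aim is not tied to an outcome. Section B lists return to the operating room, fluid collections needing a procedure, hematoma, daily drain output and time to drain removal, without ranking them. Section E.5 names drain output, time to drain removal or return to the operating room. Section E.3 says: "Our study aims to demonstrate a difference in hematoma rates as well as drain output". Its next sentence calls the study a pilot that could encourage a larger investigation.

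**The concern.** An exploratory label covers the absence of a multiplicity correction. It does not settle three other things.

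- **What a significant finding refers to.** With an open list, no ranking and no stated tail, the outcome and the sidedness could both be settled after the data are seen.
- **What the power table will show.** This table is the pilot's link to a later trial, and its content depends on which side of 0.05 each endpoint falls. Significant endpoints get an observed power and no sample size.
- **What can be concluded on hematoma.** Demonstrating a difference in a binary event with 10 per arm needs an extreme split. A non-significant result would say little about TXA either way.

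**Working it through.** **Inputs from the plan.** 10 per arm, 20 in total; threshold 0.05 per test; Mann-Whitney U; power analysis one-tailed at 80% and 0.05. The plan gives no effect size, SD, hematoma rate or number of daily tests. The total reproduces only as 10 + 10 = 20, because nothing else is stated to derive it from. Effects, correlations and rates below are assumptions.

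**1. Sidedness.** From the exact null distribution of U at 10 v 10:

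- U ≤ 23 gives two-sided p = 0.043, the two-sided cut-off.
- U ≤ 27 gives one-sided p = 0.045, the one-sided cut-off; its two-sided p is 0.089.

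So U from 24 to 27 changes verdict with the tail chosen, and therefore changes its entry in the power table.

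**2. Chance of at least one p < 0.05 with no effect.** Simulation, 20,000 trials per setting, exact two-sided cut-offs, within-patient correlation assumed 0.9 to 0.3:

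- Total output and time to removal only: about 6% to 8%.
- The same two plus seven separately tested daily outputs: about 12% to 28%.

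**3. Observed power.** With the normal approximation, one-tailed observed power = 1 − Φ(1.645 − z), where z is the observed test statistic. It depends on the p-value alone:

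- One-sided p = 0.05 (z = 1.645): 1 − Φ(0) = 50%.
- Two-sided p = 0.05 (z = 1.960): 1 − Φ(−0.315) = 62%.

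Showing it only for significant results adds selection. Simulation, normal data, 10 per arm, 200,000 trials, one-sided Mann-Whitney gate, t-based observed power:

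| Assumed true effect | True power or size | Median observed power if significant |
|---|---|---|
| 0.8 SD | 49% | about 79% |
| 0 | 4.5% | about 67% |

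Repeat runs differ by about one percentage point.

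**4. Sample size for non-significant endpoints.** Section D does not say which effect will be used. If it is the observed one, n per arm = 2(1.645 + 0.842)²/d² = 12.37/d². Needed at the true effect: 12.37/0.04 = 309, 12.37/0.16 = 77, 12.37/0.64 = 19. Among non-significant results in the right direction:

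| Assumed true effect | Median n per arm from the observed effect | Needed |
|---|---|---|
| 0.2 SD | about 111 | 309 |
| 0.4 SD | about 77 | 77 |
| 0.8 SD | about 44 | 19 |

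A result in the wrong direction has no one-tailed n at all. With no true effect, about 52% of non-significant results are of that kind.

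**5. Hematoma, 10 v 10, no TXA events.** Two-sided Fisher p for b control events = 2·C(10,b)/C(20,b):

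- b = 4: 2 × 210/4845 = 0.087.
- b = 5: 2 × 252/15504 = 0.033.

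Five v none is needed. Power if TXA prevents every event is P(X ≥ 5), with X binomial (10, control rate):

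- 10%: 0.0016, or 0.2%.
- 20%: 0.0328, or 3.3%.
- 30%: 0.1503, or 15%.

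One-sided Fisher needs 4 v 0 (p = 0.043), with power 1.3%, 12% and 35%.

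**The case against.** The strongest defence is that section D already calls the analysis exploratory and uncorrected, so a reader is warned. This stands against any demand for a multiplicity correction. A reader might also infer that the plan carries a 12% to 28% false-positive rate. The documents do not support that: it needs about seven separate daily tests, whereas daily drain output could equally be one average per patient. With only total output and time to removal tested, the rate is near nominal.

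A second tempting inference is that the planned sample sizes will be too large. That holds at 0.8 SD but reverses at 0.2 SD, and it arises only if the observed effect is used. The statistician could instead take a meaningful difference with the pilot SD.

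Third, the aims are less scattered than they look. Drain output runs through sections A, B, D, E.3 and E.5, and section B closes on drain output and time to removal alone. This stands, and it points to the natural primary outcome.

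Fourth, sections A, B and C state a belief and a question about hematoma, which a pilot may do, and E.3 adds its own pilot qualifier. They should not be read as claims to demonstrate. Only the verb in E.3 goes too far. Section D also leaves the hematoma test unclear: Fisher appears in the baseline text, and efficacy names only Mann-Whitney. A normal-approximation Mann-Whitney on these tied yes/no data would be less strict, reaching 62% one-sided at a 30% control rate with every event prevented. It is therefore too strong to say that significance is out of reach under every test.

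None of this supplies a primary outcome or a test sidedness, or justifies the observed-power column.

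**Conclusion.** The point holds as a low-cost improvement that should be made, not as an error of calculation. Two parts rest on the text alone: the any-test rule has no primary outcome or sidedness, and the power table is gated on significance. The U range of 24 to 27 is exact for untied data.

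The inflation of observed power follows from the stated rule; the 79% against 49% assumes 0.8 SD, normal data and one-sided tests. The sample-size problem is conditional on using the observed effect, and its direction varies with the true effect, so the supportable word is unreliable. The hematoma powers of 0.2%, 3.3% and 15% assume two-sided Fisher, control rates of 10%, 20% and 30%, and complete prevention by TXA, which is the most favourable effect at each rate.

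**What to change.** Make these changes before unblinding.

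1. **Section D, decision rule.** Replace the any-test wording with one named drain-output outcome and an exact two-sided Mann-Whitney test. Fix the window (section D says "Each patient will be evaluated one week, three weeks, and eight weeks following their procedure", so the one-week visit offers a natural end), the rule for output after drain removal, and the handling of withdrawals. Counting output after removal as zero is workable, but it mixes drain output with time to removal, so the choice should be explicit. Alternatively, delete the sentence and report estimates only.
2. **Other outcomes.** Report estimates with 95% confidence intervals and no significance claim. Report hematoma, seroma, fluid-collection procedures and return to the operating room as counts with exact intervals, using Fisher if a p-value is shown.
3. **Power table.** Drop observed power. Give a sample size whatever the p-value, at a difference stated beforehand and with the primary test's sidedness. For continuous endpoints use the pilot SD and its 95% interval (0.76 to 1.48 times the estimate at 18 degrees of freedom). For binary endpoints use a range of assumed control rates, since ten control patients cannot estimate one usefully.
4. **Section E.3.** For hematoma rates, change demonstrating a difference to describing the rates. Sections A, B and C can stay.

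The cost is wording and analysis only, with no added patients, visits or data. Significance can then be claimed on one outcome only. A two-sided test needs a true difference of about 1.4 SD for 80% power, against about 1.2 SD one-sided. The investigators must also commit to differences worth detecting.

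### The plan pre-specifies p-values, per-group tables and a post-hoc power table, but no between-arm effect estimate and no confidence interval for a 10-per-arm pilot

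*Combined protocol and SAP*

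**What the plan says.** The whole analysis plan is in two paragraphs of section D (Research Design and Methods) of the combined protocol and SAP.

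- **Size.** "Each group will have 10 participants", and "The trial will be stopped after inclusion of twenty patients".
- **Method.** "efficacy analysis will be conducted on the outcome variables (drain output per day, total drain output, etc.) by use of Mann-Whitney U test".
- **Criterion.** "Statistically significant findings would be for a p-value less than 0.05 on any test". Whether the Mann-Whitney test is one- or two-sided is not stated.
- **Output.** "Results of the GOF and efficacy analysis will be prepared and placed into tables for each group". The content of those tables is not specified.
- **Power table.** After the results, "power analysis will also be used to calculate the observed power for those tests with significant differences as well as to determine a sample size". The sample size applies to the endpoints that did not reach significance. The settings are: "Power analysis will be based on single tail alternative hypothesis with a power (1-B) of 80 percent and a p-value of 0.05".

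Section E.3 gives the purpose: "As a pilot study, these results could be used to encourage a larger investigation of the use of TXA in panniculectomy patients". No section names a difference in medians or means, a Hodges-Lehmann shift, a probability of superiority or a confidence interval for any outcome.

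**The concern.** Section B asks whether TXA lowers drain output and brings drain removal forward. Answering that, or deciding whether a larger study is worthwhile, takes the size of the difference and how well it is known. A Mann-Whitney p-value depends only on the ranks, so it gives neither. With 10 patients per arm the uncertainty is a main part of the result, and it is the part that the planned output omits. A non-significant result would come with nothing to show how large a benefit remains possible. A significant one would come with nothing to show how small the benefit could be.

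**Working it through.** **Inputs.** From section D: 10 per arm, Mann-Whitney test, threshold 0.05, sidedness not stated; the power analysis is one-sided with 80% power. The documents give no effect size and no SD for drain output. The stated sample size therefore cannot be reproduced, and results are in SD units.

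**1. The p-value does not fix the effect.** Take two constructed data sets of 10 v 10, the second being the first shrunk to one fifth of its spread about 600 cc. The ranks are identical, so both give U = 41 and exact two-sided p = 0.53. The Hodges-Lehmann shifts and intervals differ fivefold:

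| Data set | Shift (cc) | 95% interval (cc) |
|---|---|---|
| Wide spread | -66 | -306 to 197 |
| Narrow spread | -13 | -61 to 39 |

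**2. The interval that matches the planned test.** There are C(20,10) = 184,756 equally likely rank arrangements under the null.

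- P(U ≤ 23) = 3,996/184,756 = 0.0216, so two-sided p = 0.0433.
- P(U ≤ 24) = 4,843/184,756 = 0.0262, so two-sided p = 0.0524.

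The two-sided cut-off is therefore U ≤ 23. Inverting it gives the interval from the 24th to the 77th of the 10 × 10 = 100 ordered pairwise differences, with exact coverage 1 - 0.0433 = 95.7%.

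For a one-sided test the cut-off is U ≤ 27, with P = 8,241/184,756 = 0.0446.

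**3. Width.** In simulated normal data (20,000 to 40,000 trials per setting) the half-width of this interval is about 0.98 SD. The t interval is close: t(0.975, 18) × √(2/10) = 2.101 × 0.447 = 0.94 SD. As a share of the control mean, the t half-width is 0.94 × CV. For assumed CVs of 0.3, 0.5, 0.7 and 1.0 that is 28%, 47%, 66% and 94%.

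**4. What a non-significant result would leave open.** Same simulation:

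| True shift | Non-significant, two-sided | Non-significant, one-sided |
|---|---|---|
| 0.5 SD | about 84% | about 74% to 75% |
| 1.0 SD | about 49% | about 34% to 35% |

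At a true shift of 1.0 SD, the trials that miss on the two-sided test have a 95% limit on the side of benefit averaging about 1.7 SD. About 95% of those intervals still include a benefit of 1.0 SD or more.

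**5. Whether the power table fills the gap.**

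- *Observed power.* Under a normal approximation with a one-sided 0.05 test it is Φ(z_obs - 1.645), a function of the p-value alone. One-sided p = 0.05 gives Φ(0) = 50%. One-sided p = 0.01 gives Φ(2.326 - 1.645) = Φ(0.681) = 75%.
- *Sample size.* With the plan's settings, n per arm = 2 × (1.645 + 0.842)² / d² = 12.37 / d². Suppose the estimate is 0.5 SD (illustrative), with interval 0.5 ± 0.98, or -0.48 to 1.48 SD. The point estimate gives 12.37/0.25 = 49.5, so 50 per arm. The favourable limit gives 12.37/2.19 = 5.6, so 6 per arm. At the other limit no size would show a benefit. A single figure of 50 hides that range.

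**The case against.** The plan is silent on estimates; it does not forbid them. The tables for each group may well hold medians, and a reader could subtract them. The sample-size step for non-significant endpoints cannot be carried out without some effect estimate, so one is implied. A reader might go further and infer that this pilot cannot say how large the effect is. The documents do not support that: a crude point difference may be available. What stands is that no estimate is defined and no measure of its uncertainty is planned.

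A reader might also infer that a non-significant result will be reported as no difference. The documents never say so. Planning a sample size for exactly those endpoints treats them as possibly underpowered.

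The miss rates mostly reflect the small sample, which section D acknowledges by calling the analysis exploratory, and adding an interval would not change them. That is correct. The figures that bear directly on the omission are the half-width of about 1 SD and the limit of about 1.7 SD. The miss rates show only how often the question would arise, and they depend on a sidedness that the plan leaves open.

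The exploratory label does not excuse the omission, because estimation with its uncertainty is what exploratory data can offer a later study. Section E.3 says only that the results could encourage such a study; the sample-size step in section D is the firmer evidence that an estimate is needed.

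**Conclusion.** The concern holds as a gap in the pre-specified output. The plan commits to p-values, per-group tables of unspecified content and a post-hoc power table, with no between-arm estimate and no interval. The missing interval would reach about 1 SD either side of the estimate. With a true 1.0 SD shift, about 49% of trials (two-sided) or 34% to 35% (one-sided) would be non-significant, and the two-sided misses would on average leave benefits up to about 1.7 SD open.

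The omission itself rests on the text alone. The sizes assume normal data without ties, a pure location shift and all 20 patients analysed. Figures as a share of the control mean also need an assumed CV. The Mann-Whitney test is not invalid, and nothing in data collection has to change. The amendment should be made before analysis because it determines what the pilot can report about the size of effect.

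**What to change.** Add wording to this effect to the efficacy paragraph of section D:

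> For total drain output, time to drain removal and one named per-patient summary of daily output, the Hodges-Lehmann TXA-minus-saline difference will be reported beside the Mann-Whitney p-value, with a 95% confidence interval obtained by inverting that test. Conclusions will be worded from the interval, and non-significance will not be described as absence of effect.

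Four details need to be settled with it:

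- **Daily output** is a repeated measure from two drains per patient and ends at drain removal. Name one summary per patient, for example mean daily output over a fixed early window, and state how days after removal count.
- **Ties.** The interval is exact only without ties. Drain time in whole days will be tied, so specify a tie-handling or permutation-based interval there.
- **Sidedness.** State it for the Mann-Whitney test. The 95% interval above corresponds to a two-sided test and can disagree with a one-sided p-value.
- **Power table.** Drop observed power, and carry the estimate with its interval into the sample-size calculation.

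Hematoma and return to the operating room are event outcomes and need a different effect measure; this wording does not cover them.

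The cost is a few lines of code and one table column, with no new data or patients. The intervals will look wide, which is an accurate picture of what 20 patients can show.

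### The p-value decides which planning figure an endpoint gets: observed power after a significant result, a sample size only after a non-significant one

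*Combined protocol and SAP*

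**What the plan says.** Section D (Research design and methods) compares the arms on the drain outcomes: "efficacy analysis will be conducted on the outcome variables (drain output per day, total drain output, etc.) by use of Mann-Whitney U test". The significance rule is "Statistically significant findings would be for a p-value less than 0.05 on any test"; it does not say whether the tests are one- or two-sided.

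The power analysis then splits the endpoints by that rule. For those that reach significance, "power analysis will also be used to calculate the observed power for those tests with significant differences". For the rest, it will "determine a sample size for those efficacy endpoints that did not achieve statistical difference". On presentation: "These power estimates will accompany the results in a separate table". The settings are: "Power analysis will be based on single tail alternative hypothesis with a power (1-B) of 80 percent and a p-value of 0.05".

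No section plans a sample size for a significant endpoint, or a confidence interval for any endpoint. Results are to be tabulated by group, but no summary statistics are named. No method for observed power is given, and no effect size for the sizing. Section E.3 gives the forward use of the pilot: "these results could be used to encourage a larger investigation of the use of TXA in panniculectomy patients".

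**The concern.** A pilot of 10 per arm is useful mainly for what it tells the designers of the next trial. They need an estimate with its uncertainty, and a sample size for each endpoint they might choose. Here the p-value selects the figure instead.

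- An endpoint with p<0.05 gets observed power. That is calculated from the same data that produced the significant result, and it is shown only when those data looked favourable enough to pass.
- The same endpoint, the likeliest to be carried forward, gets no sample size. A reader who sees 80% or more beside it could conclude that 10 per arm is enough.

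What is at stake is the quality of the only planning figures that the plan specifies.

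**Working it through.** **Inputs from section D:** 10 per arm; Mann-Whitney U; significance at p<0.05; power analysis one-sided at 0.05 with a target of 80%. The plan states no power figure, effect or SD, so there is nothing to reproduce first. **Assumptions:** a true effect of 0.8 SD where one is needed; lognormal data with log-SD 0.8 as the skewed case; both sidedness readings; rank-based and t-based methods. A hit means p<0.05. Figures are for favourable hits (less drainage with TXA) unless stated.

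**1. Thresholds.** U runs from 0 to 100, high values favouring TXA. From the exact 10 v 10 distribution, a favourable hit needs U≥77 if the test is two-sided (total size 0.0433) or U≥73 if one-sided (size 0.0446). With no true effect, its chance is 2.2% or 4.5%.

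**2. Observed power from U.** Noether's approximation gives Φ(√(12×0.25×20)×(U/100−0.5)−1.645), where √60 = 7.746.

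| | Two-sided test | One-sided test |
|---|---|---|
| Lowest possible after a hit | U=77: Φ(2.091−1.645) = 67% | U=73: Φ(1.782−1.645) = 55% |
| Median hit, no true effect | U=80: Φ(2.324−1.645) = 75% | U=76: Φ(2.014−1.645) = 64% |
| Share of those hits at 80% or more | 27% | 13% |

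The null distribution of U is exact for any continuous data; the power formula is an approximation. Since this figure depends on U alone, it is a fixed function of the p-value. A two-sided hit favouring saline (U≤23) would show at most Φ(−2.091−1.645), below 0.1%.

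**3. Observed power from a t-test** (noncentral t, 18 df, one-sided 0.05, at the observed standardised difference). With no true effect, the median hit shows 78% / 66% (two-sided / one-sided test) for normal data and 70% / 60% for lognormal data (3,000,000 simulated pilots each). Among hits, its rank correlation with U is only about 0.75 (normal) and 0.5 (lognormal), so it is related to p but noisy.

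**4. Assumed true effect of 0.8 SD** (0.8 log-SDs if lognormal; 500,000 pilots each). Real one-sided Mann-Whitney power is 49%.

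| Method | Median shown after a one-sided hit | After a two-sided hit |
|---|---|---|
| Rank-based | 75% | 80% |
| t, normal | 80% | 86% |
| t, lognormal | 69% | 76% |

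Two-sided real power is 35%. Setting one-sided observed power against that would mix sidedness, so 49% is the fair comparison in both columns.

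**5. Larger effects.** For t-based power with normal data and two-sided hits, mean power shown v real one-sided t power is 85% v 53% at 0.8 SD and 90% v 82% at 1.2 SD. For lognormal data and one-sided hits, the median shown v real Mann-Whitney power is 77% v 79% at 1.2 log-SDs and 83% v 92% at 1.5. The excess shrinks and can reverse.

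**6. The missing sample size.** At 0.8 SD the endpoint hits, and so gets no N, in 49% of pilots (one-sided test) or 35% (two-sided). Among one-sided hits, 36% (rank) or 50% (t, normal) show 80% or more; among two-sided hits, 50% or 68%. The N per arm needed for 80% one-sided power is:

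- t-test: 2×(2.486/0.8)² = 19.3, but noncentral-t power at 20 is 79.94%, so 21.
- Mann-Whitney: with P = Φ(0.8/√2) = 0.714, Noether gives 2.486²/(3×0.214²)/2 = 22.5. Simulated power is already 81% at 22.

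The need is therefore about 21-22 per arm, roughly twice the pilot's 10.

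**The case against.** The analysis is openly exploratory. Section E.3 says only that the results could encourage a larger study, not that this table will size it. Nothing stops the investigators from sizing a significant endpoint later. All of this stands and limits the severity. It does not cure the defect: followed as written, the rule gives a weak figure for the endpoints that hit and no N for them, and the group tables are not specified well enough to be a sure substitute.

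A reader might infer that observed power is always inflated and merely restates the p-value. The plan names no method, so that cannot be said. The exact link to p holds for formulas in U alone, not for t-based power. Inflation is marked at small and moderate effects but not at every effect, and a hit favouring saline shows almost no one-sided power for TXA benefit.

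A reader might also infer that tests and sizing contradict each other on sidedness. The sizing is one-sided, but the tests' sidedness is unstated, so this needs clarification only. If the tests were two-sided, an N set for 80% one-sided power would have Φ(1.645+0.842−1.960) = 70%.

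Finally, a reader might infer that the sample sizes after a miss will be unstable. That follows only if the observed effect is the sizing input, which the plan does not say.

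**Conclusion.** The concern holds as a minor one. Sorting endpoints by p<0.05 gives those that hit a figure with little planning value and leaves them without a sample size. The rank-based floors of 67% / 55% and null medians of 75% / 64% rest on 10 per arm, no ties and Noether's formula, not on an assumed effect or on normality. The comparison of 69-80% shown with about 49% real power rests on the assumed 0.8 SD and a one-sided test. It illustrates a moderate effect and does not predict this trial's results. It would be wrong to conclude that the pilot itself is compromised: its size, efficacy tests and safety monitoring do not use this table.

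**What to change.** Replace the power-analysis wording in section D as follows.

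- **Drop observed power.**
- **Estimate every endpoint, whatever its p-value.** For drain endpoints, report the Hodges-Lehmann difference with an exact or tie-adjusted 95% interval for the arm sizes obtained. At 10 v 10 the limits are the 24th and 77th of the 100 ordered pairwise differences, with coverage 1−0.0433 = 95.7% under a shift model without ties. Days to drain removal will tie, and withdrawals or odd/even allocation may leave other arm sizes. For hematoma, return to the operating room and aspiration, report the risk difference with an exact interval.
- **Size every candidate endpoint, whatever its p-value,** from a relevant difference that the investigators name before unblinding. For continuous endpoints, use the pilot SD with its 95% limits: 0.76 to 1.48 times the estimate on 18 df, hence N from 0.57 to 2.19 times. These limits assume normality; with lognormal data at log-SD 0.8, the raw-scale limits cover only 58%. If outputs are skewed, use the log scale and state the difference as a ratio. For binary endpoints, use the control event rate with its interval.
- **State one sidedness** for both the tests and the sizing.

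The cost is a few sentences, with no change to patients, visits or data. The investigators lose a reassuring figure and must commit to a relevant difference in advance. They may also quote a larger future N: about 27% more if the sizing becomes two-sided, from ((1.960+0.842)/(1.645+0.842))² = 1.27.
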